5. SUBJECT ENROLLMENT

Before subjects begin participation in any study-specific activities/procedures, Amgen requires a copy of the site's written independent ethics committee/institutional review board (IEC/IRB) approval of the protocol, informed consent form, and all other subject information and/or recruitment material, if applicable (see [Section 11.2](#)). All subjects or legally acceptable representatives must personally sign and date the IEC/IRB and

Amgen approved informed consent form before commencement of study-specific activities/procedures.

A subject is considered enrolled when the investigator decides that the subject has met all eligibility criteria. The investigator is to document this decision and date, in the subject's medical record and in/on the enrollment case report form (CRF).

Each subject who enters into the screening period for the study (defined when the subject signs the informed consent) receives a unique subject identification number before any study-related activities/procedures are performed. The subject identification number will be assigned by the Interactive voice response (IVR) system. This number will be used to identify the subject throughout the clinical study and must be used on all study documentation related to that subject. Subjects who are determined not eligible after screening must be screen-failed in the IVR system and the reason for the screen-failure provided. Subjects who do not meet all eligibility criteria may be rescreened 1 time at the discretion of the investigator. Prior to rescreening, subjects may need to reconsent to the study to ensure that the IEC/IRB approved main informed consent form is signed within 28 days of enrollment. Subjects who are determined not eligible after rescreen must be screen-failed in the IVR system and the reason for the screen-failure provided. Subjects may only be enrolled once into this study.

The subject identification number must remain constant throughout the entire clinical study; it must not be changed after initial assignment, including if a subject is rescreened.

5.1 Treatment Assignment

All subjects enrolled will receive open-label talimogene laherparepvec. The treatment assignment date is to be documented in the subject's medical record and on the enrollment CRF.

6. TREATMENT PROCEDURES

6.1 Classification of Product(s) and/or Medical Device(s)

The Amgen Investigational Product (except if required by local regulation) used in this study includes: talimogene laherparepvec.

The Investigational Product Instruction Manual (IPIM), a document external to this protocol, contains detailed information regarding the storage, preparation, destruction, and administration of talimogene laherparepvec.

6.2 Investigational Product

6.2.1 Amgen Investigational Product: Talimogene Laherparepvec

Talimogene laherparepvec will be manufactured and packaged by Amgen Inc. and distributed using Amgen clinical study drug distribution procedures. Talimogene laherparepvec is supplied as a sterile frozen liquid in a single-use, 2-cc Crystal Zenith vial with a gray Fluorotec®-coated chlorobutyl elastomer stopper, aluminum seal, and polypropylene cap. Each vial contains a minimum of 1.0 mL talimogene laherparepvec at either 10⁶ PFU/mL or 10⁸ PFU/mL concentrations. The supply for the 10⁶ PFU/mL concentration will be packaged separately from the supply for the 10⁸ PFU/mL concentration. As necessary, talimogene laherparepvec 10⁸ PFU/mL will be diluted 1:10 for a concentration of 10⁷ PFU/mL immediately prior to injection.

6.2.1.1 Dosage, Administration, and Schedule

Talimogene laherparepvec must be prepared and administered by a qualified healthcare professional. Subjects should be assessed clinically for adverse events/toxicity prior to each dose using the Common Terminology Criteria for Adverse Events (CTCAE) version 4.0 ([Appendix A](#)). Complete blood count with differential and chemistry panels including liver function laboratory tests (ALT, AST, and total bilirubin) should be obtained according to the Schedule of Assessments ([Table 2](#)) and the results should be checked before each scheduled dose. Dosing will occur only if these test values are acceptable per [Section 6.2.1.2](#).

Hospitalization for < 24 hours may be allowed when subjects are administered the first dose of talimogene laherparepvec. Need for hospitalization more than 1 day should be discussed between the treating physician and the Amgen medical monitor.

Talimogene laherparepvec will be administered by intralesional injection only into injectable cutaneous, subcutaneous, and nodal tumors, with or without image ultrasound guidance. Talimogene laherparepvec must not be administered into visceral organ metastases.

On day 1 (week 0) the first dose of talimogene laherparepvec will be up to 4.0 mL of 10⁶ PFU/mL. The second injection up to 4.0 mL of 10⁸ or 10⁷ PFU/mL, should be administered 3 weeks (+ 5) days after the initial injection (ie, no sooner than day 22 but should not be delayed more than 5 days after the 3-week time point). Subsequent injections up to 4.0 mL of 10⁸ or 10⁷ PFU/mL should be given every 2 weeks (± 3) days.

The maximum volume of talimogene laherparepvec to be administered at each treatment visit is 4.0 mL. Investigators are encouraged to administer the maximum volume possible into each injected lesion based on lesion size, not to exceed 4.0 mL in any individual lesion. Dose reduction for adverse events is not allowed. However, if during the process of administering talimogene laherparepvec in the clinic, the subject cannot tolerate the full dose due to an injection-related adverse event such as pain, the total volume given should be recorded, and the reason for intolerance should be documented as an adverse event.

The volume of talimogene laherparepvec to be injected into the tumor(s) is dependent on the size of the tumor(s) and should be determined according to the injection volume guideline in Table 1. The tumor size assessment should be done by clinical exam using ruler or caliper for cutaneous and palpable and protruding subcutaneous and nodal lesions, or by measurements under ultrasound of deep-seated subcutaneous and nodal lesions.

Table 1. Talimogene Laherparepvec Injection Volume Guideline Based on Tumor Size

Tumor Size (longest dimension)	Maximum Injection Volume
> 5.0 cm	4.0 mL
> 2.5 cm to 5.0 cm	2.0 mL
> 1.5 cm to 2.5 cm	1.0 mL
> 0.5 cm to 1.5 cm	0.5 mL
≤ 0.5 cm	0.1 mL

On each treatment day, prioritization of injections is should be as follows:

- any new injectable tumor that has appeared since the last injection
- by tumor size, beginning with the largest tumor

The lesions injected and volume will be recorded on the CRF.

A subject will be treated with talimogene laherparepvec until the subject has a DLT during the DLT evaluation period, subject has achieved a CR, no injectable lesions, clinically relevant (resulting in clinical deterioration or requiring change of therapy) disease progression beyond 24-week of treatment, per modified WHO response criteria (see [Appendix D](#)), or safety concern, **a maximum treatment duration of 48 months, or the drug is commercially available in Japan**, whichever occurs first. Due to the mechanism of action, subjects may experience growth in existing tumors or the

appearance of new tumors prior to maximal clinical benefit of talimogene laherparepvec. Therefore, treatment with talimogene laherparepvec should be continued for at least 24-weeks even in the presence of progression, including the appearance of new lesions to allow for delayed-immune-based anti tumor effects to occur unless other therapy for melanoma is required. After 24 weeks, subjects will remain on treatment until clinically relevant disease progression occurs as defined in [Appendix D](#).

The dose, lesion site, start date, and lot number of talimogene laherparepvec are to be recorded on each subject's CRF.

6.2.1.2 Dose-cohort Study De-escalation and Stopping Rules

6.2.1.2.1 Rules for DLT Evaluation

The DLT evaluation period is 35 days from the first dose of talimogene laherparepvec. To be evaluable for a DLT, subjects must have received at least 1 dose of talimogene laherparepvec and had the opportunity to be followed for the entire DLT evaluation period or have experienced a DLT within the DLT evaluation period. To obtain the first 6 DLT-evaluable subjects, subjects will be replaced if they are not evaluable for DLT (eg, a subject did not receive study treatment, or ended the study treatment before completion of DLT evaluation period for a reason other than experiencing a DLT).

A DLRT composed of the investigator(s), Amgen Medical Monitor, Amgen Global Safety Officer or designated safety scientist, Amgen Clinical Research Study Manager and Amgen Biostatistics representative will review data, monitor safety, and make dose and dose de-escalation decisions. Additional members may be added to the DLRT as needed (eg, Global Development Leader) (see [Section 10.3.2](#)). The DLRT will review the safety data after 6 DLT-evaluable subjects have been enrolled at Dose 1 (see below). Enrollment will be temporarily paused during the DLT review period to evaluate the 6 DLT-evaluable subjects. The decision to continue to enroll 12 additional subjects at the Dose 1 will be based on observing < 33% subject incidence of a DLT in the initial 6 subjects during the DLT evaluation period.

If at any time there are 2 or more subjects with a DLTs prior to enrollment of the first 6 DLT-evaluable subjects, an ad hoc DLRT meeting will be convened to determine if dose de-escalation (Dose -1) is required. The safety data during the enrollment of the additional subjects will be monitored on an going basis and an ad hoc DLRT meeting may be called, if needed, to determine the further course of the study.

Dose De-escalation

If dose de-escalation is needed, then the remaining subjects will be treated at the lower dose regimen of talimogene laherparepvec (Dose -1).

Dose	Initial dose	Subsequent doses
1	10^6 PFU/mL (day 1, week 0)	10^8 PFU/mL (3 weeks later and then every 2 weeks thereafter)
-1	10^6 PFU/mL (day 1, week 0)	10^7 PFU/mL (3 weeks later and then every 2 weeks thereafter)

Dose -1 will be administered as an initial dose up to 4.0 mL of 10^6 PFU/mL (day 1, week 0) followed by dose of up to 4.0 mL of 10^7 PFU/mL 3 weeks later (+ 5 days). Subsequent doses of up to 4.0 mL of 10^7 PFU/mL will be administered every 2 weeks (\pm 3 days) thereafter.

The DLRT will review the safety data after the first 6 DLT-evaluable subjects at Dose -1 have been enrolled. Enrollment will be temporarily paused during the DLT review period to evaluate the 6 DLT-evaluable subjects at Dose -1. Upon demonstration of safety, additional subjects will be enrolled (up to a total of 18 subjects) at Dose -1 to obtain additional safety data.

The safety data of the subjects enrolled at the Dose-1 level will be monitored on an ongoing basis and an ad hoc DLRT meeting may be called, if needed, to determine the further course of the study.

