6.2.2 Dosage Adjustments, Delays, Rules for Withholding or Restarting, Permanent Discontinuation

Dose reduction for adverse events is not allowed. However, if during the process of administering talimogene laherparepvec in the clinic, the subject cannot tolerate the full dose due to an injection-related adverse event such as pain, the total volume given should be recorded, and the reason for intolerance should be documented as an adverse event.

If talimogene laherparepvec treatment is delayed by > 1 week, that dose will be deemed to have been missed and the subject will proceed to the next scheduled treatment visit.

If talimogene laherparepvec dosing is delayed by more than 4 weeks from the date of the planned dose (ie, approximately 6 weeks from the previous dose) due to the occurrence of an adverse event that is considered related to talimogene laherparepvec, the subject must be permanently withdrawn from talimogene laherparepvec treatment.

If talimogene laherparepvec dosing is delayed by more than 4 weeks from the date of the planned dose (ie, approximately 6 weeks from the previous dose) for reasons other than treatment-related toxicity, the case must be reviewed by the Amgen medical monitor in conjunction with the investigator to determine if the subject can resume talimogene laherparepvec therapy.

Talimogene laherparepvec will be permanently discontinued if a subject has a DLT during the DLT evaluation period, subject achieved a CR, no injectable lesions, clinically relevant (resulting in clinical deterioration or requiring change of therapy) disease progression beyond 24-weeks of treatment, per modified WHO response criteria (Appendix D), or safety concern (refer to [Section 8.1](#)), **reaches a maximum treatment duration of 48 months, or the drug becomes commercially available in Japan**, whichever occurs first.

For additional information, related special warnings, and precautions for the use of talimogene laherparepvec please refer to the latest version of the talimogene laherparepvec Investigator's Brochure.

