7.2.3 Treatment

Visits will occur per the Schedule of Assessments ([Table 2](#)) during the treatment period from day 1 (week 0). On-study visits may be completed within \pm 3 days of the planned visit date. The date of the first dose of talmogene laherparepvec is defined as day 1 (week 0). All subsequent doses and study visits will be scheduled based on the day 1 (week 0) date. Study treatment should begin as soon as possible after enrollment via the IVR system but no later than 5 days after enrollment. Administration of talmogene

laherparepvec is to be performed after all other procedures are completed during each visit that it is required, unless otherwise stated. It is recommended that dosing occur on the same day of the week (eg, if first dose is administered on Monday, all subsequent doses should be administered on a Monday). A + 5 day dosing window is allowed at week 3. Subsequently a \pm 3-day dosing and study procedure window is allowed.

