7.1 DLT Analysis Set

The DLT analysis set will include DLT-evaluable subjects defined as subjects who had the opportunity to be followed for at least 35 days on treatment from the initial dosing (unless discontinued due to DLT) and received at least one dose of talimogene laherparepvec. Subjects may be replaced in a cohort if they are not evaluable for DLT (eg, a subject did not receive study treatment, or ended the study treatment before completion of DLT evaluation period for a reason other than experiencing a DLT).

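### One shared first dose makes a subject DLT-evaluable, so someone who misses the week-3 injection can count as 'no DLT' with 0-3 days at the cohort's concentration

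*Protocol*

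**What the plan says.** Protocol 6.2.1.2.1 sets the window: "The DLT evaluation period is 35 days from the first dose of talimogene laherparepvec". A subject is evaluable after a DLT in that window; otherwise "subjects must have received at least 1 dose of talimogene laherparepvec and had the opportunity to be followed for the entire DLT evaluation period". Non-evaluable subjects are replaced. The examples given are subjects never treated and subjects who "ended the study treatment before completion of DLT evaluation period for a reason other than experiencing a DLT".

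SAP 7.1 is parallel. It includes subjects who "had the opportunity to be followed for at least 35 days on treatment from the initial dosing" (unless they stopped for a DLT) "and received at least one dose of talimogene laherparepvec".

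Under 6.2.1.2.1 the initial dose is 10^6 PFU/mL for both dose levels. The levels separate at the second injection (10^8 against 10^7 PFU/mL), which 6.2.1.1 places "no sooner than day 22 but should not be delayed more than 5 days after the 3-week time point".

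If a dose is more than 1 week late, 6.2.2 says "that dose will be deemed to have been missed and the subject will proceed to the next scheduled treatment visit". Section 7.2.3 fixes that visit: "All subsequent doses and study visits will be scheduled based on the day 1 (week 0) date".

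Protocol 10.2.1.1 and 10.3.2 call a dose level safe when 0 or 1 DLT is seen in the first six evaluable subjects.

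**The concern.** The dose needed for evaluability is the one dose that cannot tell the two levels apart. The definition sets no minimum exposure to the concentration on which the Dose Level Review Team (DLRT) is deciding.

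Most routes to an uninformative subject are closed, because untreated subjects and those who end treatment early are replaced. One narrow route stays open: the subject remains on treatment, the week-3 dose is deemed missed, and dosing resumes at week 5. That subject meets both definitions and enters the count as a non-event, although nearly all of the observation follows the shared first dose. Some DLT criteria in 6.2.1.2.2 also need time to be met: grade 3 non-hematologic toxicity lasting more than 3 days, or a laboratory abnormality persisting more than 1 week. Neither duration can run its course in the 0-3 days left, and the documents do not say whether duration beyond the window counts.

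At stake is a six-person decision that moves toward 'safe' when the true risk at the cohort's concentration is high.

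**Working it through.** **1. Days left in the window.** Inputs: day 1 is the first dose; week 3 is day 22, up to 5 days late; week 5 is day 36 ± 3 days, anchored to day 1. The text allows the window to end on day 35 (counting day 1) or day 36 (adding 35 days). Days left = last day of window − day of injection.

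| First injection at cohort concentration | Days left, end day 35 | Days left, end day 36 |
|---|---|---|
| Week 3, day 22 | 13 | 14 |
| Week 3, day 27 | 8 | 9 |
| Week 3, 1 week late (day 29, counted from day 22) | 6 | 7 |
| Week 5, earliest (day 33) | 2 | 3 |
| Week 5, nominal (day 36) | outside | 0 |
| Week 5, latest (day 39) | outside | outside |

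A dose late by 1 week or less is not missed and leaves about a week. A missed week-3 dose leaves 0-3 days. (The synopsis gives ± 5 days for this injection where 6.2.1.1 gives + 5; these should be reconciled, but the result does not depend on it.)

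**2. Table 4 reproduced.** P(safe) = (1−p)^6 + 6p(1−p)^5.

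- p = 0.10: 0.5314 + 0.3543 = 0.886 (stated 89%)
- p = 0.30: 0.1176 + 0.3025 = 0.420 (stated 42%)
- p = 0.50: 1/64 + 6/64 = 0.109 (stated 11%)

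**3. One of six affected.** Read p as the DLT rate with the cohort's concentration given in the window. Give the affected subject only a first-dose risk q. Then P(safe) = A + B − qB, where A = (1−p)^5 and B = 5p(1−p)^4. The documents do not split risk between injections, so q is an assumption, run from zero to half of p.

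| p | A | B | q = 0 | q = p/2 |
|---|---|---|---|---|
| 0.10 | 0.5905 | 0.3281 | 0.919 | 0.902 |
| 0.30 | 0.1681 | 0.3602 | 0.528 | 0.474 |
| 0.50 | 0.0313 | 0.1563 | 0.188 | 0.148 |

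So 42% becomes 47-53% at a true 30%, 11% becomes 15-19% at 50%, and 89% becomes 90-92% at 10%.

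**4. Averaged over an assumed miss rate.** No missed-dose rate is given. If each subject independently misses with probability m, the rate per counted subject is r = p(1−m) + qm, and P(safe) = (1−r)^6 + 6r(1−r)^5, with q from p/2 to zero.

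- m = 5%, p = 0.30: r = 0.2925 to 0.285, P(safe) 44-45%
- m = 10%, p = 0.30: r = 0.285 to 0.270, P(safe) 45-49%
- m = 5%, p = 0.50: r = 0.4875 to 0.475, P(safe) 12-13%
- m = 10%, p = 0.50: r = 0.475 to 0.450, P(safe) 13-16%

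The chance that exactly one of six is affected, 6m(1−m)^5, is 23% or 35%.

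**The case against.** **Table 4 needs no correction.** Protocol 10.2.1.1 describes true rates for the protocol therapy, and that therapy includes the skip rule in 6.2.2. If p is the 35-day rate among evaluable subjects treated per protocol, Table 4 is right as it stands. This objection holds. A reader might infer that the published operating characteristics are wrong; the documents do not support that. The shift in steps 3 and 4 appears only under the other reading of p.

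**Safeguards exist.** The replacement examples are not an exhaustive list, the DLRT reviews product administration data (10.3.2), and safety is monitored through the next 12 subjects (3.1). These lower the risk of a poor decision. None is a rule that makes this subject non-evaluable or changes how the subject is counted.

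**SAP 7.1 speaks of time on treatment.** Skipping one dose under 6.2.2 is not ending treatment, so the phrase does not exclude the subject. Nor does it support an inference that the SAP contradicts the protocol: the two agree on the one-dose requirement.

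**Toxicity-driven misses would already be DLTs.** Many would. What remains is mainly logistical misses, lower-grade related events, and exceptions such as grade 3 fatigue. Protocol 2.2 reports that most adverse events in the phase 3 study were mild or moderate and generally resolved within 72 hours. That makes the open route uncommon but does not close it.

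**Conclusion.** The gap is real, narrow and cheap to close; severity is low. Under the stated rules, a subject who stays on treatment and is deemed to have missed week 3 counts as a non-event with 0-3 in-window days at the concentration being judged.

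With one of six affected, the probability of declaring the dose safe rises by about 5 to 11 points at a true 30% rate and by about 4 to 8 points at 50%. This rests on three assumptions: p is the rate at the cohort's concentration, first-dose risk lies between zero and half of p, and one subject is in fact affected. Averaged over an assumed 5% miss rate, the shift is about 2 to 3 points at both rates. The documents allow no firmer estimate because they give no missed-dose rate.

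It would go too far to say that a dose was, or would be, wrongly declared safe. Nothing in the documents shows that any of the first six missed week 3.

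**What to change.** **If the first-six decision is still open**, amend protocol 6.2.1.2.1 and SAP 7.1 together:

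- For that decision, a DLT-evaluable subject either had a DLT in the window, or received the week-3 injection at the cohort's concentration (not deemed missed under 6.2.2) and was followed to the end of the window.
- The sponsor states the window's last day (35 or 36) and the minimum follow-up required after that injection. Requiring merely any in-window injection would still admit a first cohort-concentration dose on days 33-35.
- Under the existing replacement rule, subjects who missed the week-3 injection are replaced only if the reason was unrelated to study-drug toxicity.
- Subjects whose week-3 dose was withheld for related toxicity stay evaluable, remain among the six, and are flagged to the DLRT. Replacing them would bias the count toward 'safe'.

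**If the decision has already been made**, leave the analysis-set definition unchanged; redefining a primary-endpoint set after open-label data are known would be worse than the gap. Add one sensitivity row to the DLT table: incidence among subjects who had a DLT or received the week-3 injection (not deemed missed).

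Protocol 10.1.1.4.1 cites 6.2.1.2.2 for evaluability, which is defined in 6.2.1.2.1; correct this in the same edit.

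Cost: wording in two places, with possibly one or two replacements and a short delay before the DLRT meeting, or one extra table row. No dose, schedule or DLT criterion changes.

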6.2.1.2.2 Definition of DLT

All toxicities will be graded using the CTCAE version 4.0 (see [Appendix A](#)). The occurrence of any of the following toxicities during the DLT evaluation period will be considered a DLT, if judged by the investigator to be related to the administration of talimogene laherparepvec:

- grade 4 non-hematologic toxicity
- grade 3 non-hematologic toxicity lasting > 3 days despite optimal supportive care
 - grade 3 fatigue will not be classified as DLT, irrespective of duration
- Any grade 3 or higher non-hematologic laboratory value reported as an adverse event if:
 - medical intervention is required, or
 - the abnormality leads to hospitalization, or
 - the abnormality persists for > 1 week (Laboratory values that persist for > 1 week but are deemed not clinically important per both investigator and sponsor will not be considered DLTs)
- Febrile neutropenia grade 3 or grade 4

- Thrombocytopenia $< 25 \times 10^9/L$ associated with bleeding event requiring intervention
- Serious herpetic event (eg, herpetic encephalitis, encephalomyelitis, or disseminated herpetic infection)
- grade 5 toxicity (ie, death)
- Any other intolerable toxicity leading to permanent discontinuation of talimogene laherparepvec

If a subject experiences a DLT during the DLT evaluation period, study treatment will be discontinued for that subject.

